**Table 3: Table of Laboratory Assessments**

[figure not shown]
	Screening	Baseline	Day 1	Weeks 1,2, 3,5,6,7,10, 14, 18, 28 and q 4 weeks thereafter	Week 4	Week 8	Week 12	Week 16	Week 20	Week 24	Extension Phase Visits (q12 weeks after Week 24)	End of Treatment or Early Termination Visit (EOT)	Follow-Up 30 to 37 days after last dose of ruxolitinib or EOT visit
Laboratory Assessment	Day -28 to -8	Day -7 to -1	Day 1	± 3 days	± 5 days	± 5 days	± 5 days	± 5 days	± 5 days	± 5 days	± 5 days	± 5 days	
Serum Chemistry	X	X			X	X	X	X	X	X	X	X	X
Hematology	X	X		X	X	X	X	X	X	X	X	X	X
Coagulation panel	X	X				X				X	X	X	X
Lipid Panel		X			X		X			X	X	X	X
Serum Pregnancy Test a	X												X
Urine Pregnancy Test a		X			X	X	X	X	X	X	X	X	
Serology for HIV, HBV, HCV	X												
Urinalysis		X								X	X	X	X

a Women of childbearing potential only.

### 4.3. Sample Size Considerations

Approximately 150 subjects will be enrolled in order to assess (on the efficacy side) the dose-effect correlation (between percent changes from baseline in spleen volume/total symptom score at Week 24 and final titrated dose level). Using an alpha of 5% (2-sided), this sample size gives a power of 96% to reject the null hypothesis of no dose-effect correlation if the true correlation is 0.30. The power is 87% if the true correlation is 0.25, and the power is 69% if the true correlation is 0.20. These calculations are based on [Cohen 1988](#), Formula 12.3.4. SAS procedure POWER is used and the power curves are displayed in Figure 1.

**Figure 1: Power and Sample Size Curves for 3 Alternative Hypotheses on the Level of Dose-Effect Correlation**

It is noted that the above sample size calculation is based on the rationale that the first primary endpoint (correlation between percent change from baseline in spleen volume at Week 24 by the final titrated dose) is powered following the procedure of the sequential test used for this study (see [Section 5.4.2](#)). At the given sample size, power can also be assessed for the second co-primary endpoint (correlation between percent change from baseline in total symptom score at Week 24 by the final titrated dose).

In addition, the mean percent change from baseline in spleen volume measured by MRI, and mean percent change from baseline in total symptom score at Week 24 will each be estimated with a 95% confidence interval. With 150 subjects, the half-length of the 95% confidence

interval of the change from baseline in spleen volume at Week 24 is approximately 3%. This is based on the Phase 3 study (INCB 18424-351), where the standard deviation of the percent change from baseline in spleen volume at Week 24 was 19%.

## **5. DATA HANDLING DEFINITIONS AND CONVENTIONS**

### **5.1. Scheduled Analyses**

In addition to the planned final CSR analysis, interim data reviews by the DMC focused on events of thrombocytopenia and hemorrhage on predefined schedules are planned.

- 28 days after 20 subjects have enrolled.
- 28 days after 40 subjects have enrolled.
- Other reviews can be scheduled only if the DMC deems it necessary that additional data would need to be reviewed to assess safety parameters as specified by the protocol.

Since all interim data reviews are focused on safety only, there is no alpha-spend of the final CSR efficacy analysis.

#### **5.1.1. First DMC Data Review Meeting**

When the 20th patient is enrolled, additional screening of subjects will be paused for at least 28 days and up to approximately 42 days. Subjects in screening at that time will be allowed to enroll if they are found to be eligible. During this period, enrolled subjects will be allowed to continue on study per the protocol. At least 28 days from the enrollment of the 20th subject, safety data will be assessed by the DMC and the sponsor. Subjects will be analyzed if they have completed at least 28 days on the study or have discontinued the study because of Grade 4 thrombocytopenia or > Grade 2 hemorrhage. Demographics, baseline characteristics, and dose exposure will be summarized for those subjects. Also AE and laboratory parameters will be analyzed.

#### **5.1.2. Second DMC Data Review Meeting**

At least 28 days from the enrollment of the 40th subject, safety data will be assessed by the DMC and the sponsor. Since the first dose escalation opportunity in the study is at Day 28 and the starting dose for all subjects of 5 mg bid will have been adequately assessed for safety at the first safety review after the enrollment of 20 patients, screening will not be suspended following enrollment of the 40th subject. If safety of the 5 mg bid dose is not clear from this first data review, the DMC and the sponsor may mandate a hold on screening at the review that occurs with enrollment of the 40th subject. Subjects will be analyzed when they have completed at least 28 days on the study or discontinued due to Grade 4 thrombocytopenia or > Grade 2 hemorrhage. Demographics, baseline characteristics, and exposure will be summarized for those subjects. Also AE and laboratory parameters will be analyzed.

More details were described in the protocol Section 11.7, Data Safety Monitoring and the corresponding DMC charter.

## 5.2. Treatment Groups

Subjects will be summarized as 1 group regardless of dose titration. For certain summaries of AEs by dose received (details can be found in the appendix of table shells), subjects will be grouped into the following categories:  $\leq 5$  mg,  $> 5$  to 10 mg,  $> 10$  to 15 mg,  $> 15$  to 20 mg,  $> 20$  to 25 mg, and  $> 25$  mg based on the final titrated total daily dose (see [Section 5.9.3.1](#)).

In addition, for the summary of exposure, final titrated dose groups as defined above may be used as treatment groups and additional efficacy analysis may utilize these dose categories.

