### 5.9.3. Dosing Level and Compliance

#### 5.9.3.1. Final Titrated Dose Level

The analytic value of the last titrated dose level will be derived as the average of the total daily dose (excluding periods of dose interruption) during the time interval of Day 141 and Day 168, or the last 28 days of available dosing data (for subjects who discontinued treatment early). All available data points in the time interval will be used for this calculation.

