#### 5.9.3.2. Last Average Daily Dose Level During the Treatment Period

For subjects who have the analytic value of the last titrated dose level derived, the last average daily dose level during the treatment period will be the same. For subjects who discontinued and do not have last titrated dose level derived, it will be the average of the last 28 days (excluding periods of dose interruption) of treatment. For subjects who discontinued study before Day 28, it is the same as the average daily dose level during the study.

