### **5.9.3.3. Study Drug Compliance**

Study drug compliance (%) is calculated as

$$100 \times [\text{total dose taken}]/[\text{total dose prescribed}]$$

where total dose taken is calculated as before, and total dose prescribed will be based on the dosing prescription as collected through the CRF pages of EX domain. If prescribed dose collected from EX domain is 0, it also indicates a prescribed dose interruption; in addition, dose reduction or increase as recorded in EX domain are all regarded as investigator-mandated prescriptions on study drug for the subjects to follow.

Study drug compliance will be calculated only for the pre-extension phase of 24 weeks. Based on need of exploratory analysis, compliance for other periods may be derived as well.

Because of the eCRF design, other than calculating study drug compliance, data collected on the EX domain of the eCRF will be used as actual study drug administration information in order to carry out other dose-response type analyses, such as AEs by the dose level before the AE (Section 5.9.3.4). In the case of a serious discrepancy between the prescribed dose and the dose received, additional actions may be taken to modify data entries.

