### **5.9.3.4. Last Dose Level Prior to an Adverse Event**

The last dose level prior to an AE is derived as the last non-zero dose (from EX domain) prior to the day an AE occurred. The reason to use “prior to the day” which excludes the day on which an AE occurred is that daily dose is divided into morning and evening doses and no dose administration time is collected on eCRF, making the last dose prior to an AE difficult to verify if “on the same day” dose levels are also included in the derivation.

It is noted that the data collected through the EX domain is treated as actual doses (rather than the prescribed dose schedule, as is the case of deriving compliance, defined earlier). This approach is used throughout when dose-response analyses (for both safety and efficacy) are carried out.

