14.3.2.8	Summary of Subjects Reporting Treatment-Emergent Adverse Events (All Causalities) Leading to On-Study Death by MedDRA System Organ Class, Preferred Term, and Dose Level Ever Received	Safety
Safety: Laboratory Data		
14.3.3.1.1	Summary of Laboratory Values – Hematology	Safety
14.3.3.1.2	Shift Summary of Laboratory Values in Normal Ranges - Hematology	Safety
14.3.3.2.1	Summary of Laboratory Values – Serum Chemistry	Safety
14.3.3.2.2	Shift Summary of Laboratory Values in Normal Ranges – Serum Chemistry	Safety
14.3.3.3.1	Summary of Laboratory Values – Coagulation	Safety
14.3.3.3.2	Shift Summary of Laboratory Values in Normal Ranges – Coagulation	Safety
14.3.3.4.1	Summary of Laboratory Values – Urinalysis	Safety
14.3.3.4.2	Shift Summary of Laboratory Values in Normal Ranges – Urinalysis	Safety
14.3.3.5.1	Shift Summary of Laboratory Values in CTC Grade - To the Worst Abnormal Value (Tests with One Directional CTC Grade)	Safety

Table Number	Title	Population
14.3.3.5.2	Shift Summary of Laboratory Values in CTC Grade - To the Worst Abnormal Value (Tests with Two Directional CTC Grade)	Safety
14.3.3.6.1	Summary of Subjects with Treatment Emergent Thrombocytopenia of Grade 4 as Derived From Laboratory Data by Dose Level Ever Received	Safety
14.3.3.6.2	Summary of Subjects with Treatment Emergent Anemia of Grade 4 as Derived From Laboratory Data by Dose Level Ever Received	Safety
Safety: Vital Signs		
14.3.4.1	Summary of Systolic Blood Pressure	Safety
14.3.4.2	Summary of Diastolic Blood Pressure	Safety
14.3.4.3	Summary of Heart Rate	Safety
14.3.4.4	Summary of Respiratory Rate	Safety
14.3.4.5	Summary of Body Temperature	Safety

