14.3.3.1.2	Shift Summary of Laboratory Values in Normal Ranges - Hematology	Safety
14.3.3.2.1	Summary of Laboratory Values – Serum Chemistry	Safety
14.3.3.2.2	Shift Summary of Laboratory Values in Normal Ranges – Serum Chemistry	Safety
14.3.3.3.1	Summary of Laboratory Values – Coagulation	Safety
14.3.3.3.2	Shift Summary of Laboratory Values in Normal Ranges – Coagulation	Safety
14.3.3.4.1	Summary of Laboratory Values – Urinalysis	Safety
14.3.3.4.2	Shift Summary of Laboratory Values in Normal Ranges – Urinalysis	Safety
14.3.3.5.1	Shift Summary of Laboratory Values in CTC Grade - To the Worst Abnormal Value (Tests with One Directional CTC Grade)	Safety
14.3.3.5.2	Shift Summary of Laboratory Values in CTC Grade - To the Worst Abnormal Value (Tests with Two Directional CTC Grade)	Safety

PROTOCOL: INCB 18424-258  
 DRUG/INDICATION: Ruxolitinib/Myelofibrosis

(Page 1 of 1)  
 VERSION: Final

Table 14.3.3.6.1

Summary of Subjects with Treatment Emergent Thrombocytopenia of Grade 4 as Derived from Laboratory Data  
 by Last Dose Before Onset  
 (Population: Safety Evaluable Subjects)

MedDRA Preferred Term	All Subjects (N=xx)	Dose Level (mg) Subjects Ever Received					
		<=5	>5 10	>10 15	>15 20	>20 25	>25
		N=xx	N=xx	N=xx	N=xx	N=xx	N=xx
Number (%) of Subjects With Grade 4 Thrombocytopenia [1]	xx ( xx.x)	xx xx%	xx xx%	xx xx%	xx xx%	xx xx%	xx xx%

PROGRAM\OUTPUT: T\_xxxx.SAS\T\_xxxxx.LST

DATE (TIME) : DDMMYY (HH:MM)

Treatment-Emergent AEs: AEs that began or worsened from baseline following the first administration of study drug.

Note: Subjects are counted only once under in the lowest dose group.

Note: N=the number of subjects who ever took a dose within the dose group, based on which the percent is calculated.

Note: AEs that occurred following the date of treatment crossover were not included.

[1] Grade 4 Thrombocytopenia is defined as any occurrence of a treatment emergent hematology lab below 25 GI/L

Reference: Listing 16.2.8.1.4

PROTOCOL: INCB 18424-258  
DRUG/INDICATION: Ruxolitinib/Myelofibrosis

(Page 1 of 1)  
VERSION: Final

Table 14.3.3.6.2

Summary of Subjects with Treatment Emergent Anemia of Grade 4 as Derived from Laboratory Data  
by Last Dose Before Onset  
(Population: Safety Evaluable Subjects)

NOTE TO THE PROGRAMMER: similarly program this as Table 14.3.3.6.1, just need to update footnote about G4 anemia.

NOTE: the following vital sign tables will be programmed according to standard output.

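### SAP 5.2 groups AE-by-dose summaries on the final titrated dose, which can post-date the event and contradicts 5.9.3.4 and the AE shells; the labels of Table 14.3.3.6.1 also disagree

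*SAP*

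**What the plan says.** SAP 5.2 reports subjects as one group, except that for some AE-by-dose summaries it assigns them to six bands (up to 5, >5 to 10, >10 to 15, >15 to 20, >20 to 25 and >25 mg) "based on the final titrated total daily dose". It refers to the table shells for details and allows the same bands for exposure and efficacy.

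SAP 5.9.3.1 defines the final titrated dose as the mean total daily dose from Day 141 to Day 168, leaving out interruptions, or over "the last 28 days of available dosing data (for subjects who discontinued treatment early").

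Other parts of the SAP use a different dose for AEs:

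- 5.9.3.3 says the dosing records will serve dose-response analyses, "such as AEs by the dose level before the AE".
- 5.9.3.4 defines the dose for an AE: it is "derived as the last non-zero dose (from EX domain) prior to the day an AE occurred".
- 8.1 plans selected maximal-severity AE tables by the dose the subject received.
- In Appendix B, shells 14.3.2.1 and 14.3.2.2.2 are titled by dose ever received. A note to 14.3.2.2.2 makes the denominator everyone who ever took a dose in the band.

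Table 14.3.3.6.1 is listed in SAP 10.1 as "Summary of Subjects with Treatment Emergent Thrombocytopenia of Grade 4 as Derived From Laboratory Data by Dose Level Ever Received". Its shell title ends "by Last Dose Before Onset" and its column head is "Dose Level (mg) Subjects Ever Received". One note counts each subject once, in the lowest dose group. Another excludes events after a treatment crossover.

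**The concern.** A grouping fixed late in the core phase is being used to classify events that may come months earlier. The event itself can also change that grouping. Protocol 8.6.2 requires a hold when platelets fall below 25 x 10^9/L, and 8.6.3.1 restarts at 5 mg qd. A Grade 4 platelet count can therefore lower the dose under which it is later displayed. In the other direction, everyone starts at 5 mg bid with no increase before the Week 4 visit (Protocol 8.6.1), so early events in subjects later titrated up would appear under a dose not yet taken.

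A dosing strategy for patients with low platelets is a stated secondary objective, and new-onset Grade 4 thrombocytopenia is a named safety endpoint. The by-dose tables are the planned displays that connect the two. A programmer working from 5.2 and one working from the shells would fill different columns.

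**Working it through.** **1. Which rule do the shells follow?** Shell 14.3.2.1 carries figures from draft DMC output, marked as illustrative, so only their structure is used here.

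- Percentages reproduce as n divided by band N. Subjects with a TEAE: 1/2 = 50.0%, 3/23 = 13.0%, 5/14 = 35.7%, 1/7 = 14.3%, 0/1 = 0.0%; overall 10/23 = 43.5%.
- Band Ns: 2 + 23 + 14 + 7 + 1 = 47, against 23 subjects (47/23 = 2.04).
- Final-dose grouping puts each subject in one band, so its Ns could not exceed 23 in total. The shell bands overlap, which fits dose ever received.
- Numerators: 1 + 3 + 5 + 1 + 0 = 10, the overall count. Each subject is counted once in that row.

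**2. Timing.** For a subject treated through Week 24, Days 1 to 140 precede the 5.9.3.1 window: 140/168 = 83% of the core phase. An AE on Day 28 falls 141 - 28 = 113 days before the window opens.

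**3. Downward shift.** Take a Grade 4 count on Day 90 at 10 mg bid (20 mg/day, band >15 to 20) and a restart at 5 mg qd on Day 105. Protocol 8.6.3.1 requires at least two weeks before an increase, so the earliest is Day 119. With a constant dose throughout Day 141 to 168:

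| Dose in window | Band under 5.2 | Band under 5.9.3.4 | Shift |
|---|---|---|---|
| 5 mg/day | up to 5 | >15 to 20 | 3 lower |
| 10 mg/day | >5 to 10 | >15 to 20 | 2 lower |
| 15 mg/day | >10 to 15 | >15 to 20 | 1 lower |
| 20 mg/day | >15 to 20 | >15 to 20 | none |

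If the restart is on Day 135 with 10 mg/day from Day 149, the window holds 8 days at 5 mg and 20 days at 10 mg: (8 x 5 + 20 x 10)/28 = 240/28 = 8.57 mg/day. The band is >5 to 10, two lower.

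The 5 mg/day row involves no increase. The other rows and the split-window case have increases after Week 16 (Day 112), so they assume the current protocol's re-escalation rules. SAP 4.1, written for Amendment 1, bars increases after Week 16 while also allowing re-escalation as platelets improve.

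**4. Upward shift.** An AE before the Week 4 visit occurs at 10 mg/day (>5 to 10 under 5.9.3.4). If the subject averages 20 mg/day in the window, 5.2 prints it under >15 to 20, two columns higher. Protocol 4.1.5 reports that most interim subjects reached 10 mg BID or higher by Week 24.

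**5. Table 14.3.3.6.1.** The list title and column head name dose ever received. The shell title names the last dose before onset. The note names the lowest dose group. If that note means the lowest dose at which a Grade 4 count occurred, it matters only for subjects with repeat Grade 4 events at different doses. Table 14.3.3.6.2 is programmed from the same shell. The crossover note has no application, because Protocol 8.3 describes a single-arm study.

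**The case against.** The strongest reply is that the rest of the SAP already settles the matter. Section 5.2 itself speaks of dose received and defers to the shells. Sections 5.9.3.3, 5.9.3.4 and 8.1 and the by-dose AE table titles in 10.1 all point away from the final titrated dose, and the draft DMC figures overlap as an ever-received display would. A programmer may well follow the shells and never produce the misattributed table. This stands. It limits the practical risk, but 5.2 still states a rule that the SAP contradicts elsewhere.

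It is also fair to say that ever received and last dose before onset need not be rivals. An onset-dose numerator over an ever-received denominator is coherent. What remains in Table 14.3.3.6.1 is that its titles, column head and note do not say so.

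A reader might infer that the column shifts measure error in tables the sponsor will print. They do not. They show what literal use of 5.2 would do, and no AE shell is laid out that way.

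**Conclusion.** The contradiction is real and minor. Literal use of 5.2 can move an event one to three columns down or two columns up in the examples. It does not always do so: a subject back at the onset dose throughout the window is unmoved, and an event inside the averaging window may be too.

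Only the descriptive AE-by-dose and Grade 4-by-dose tables are affected. The documents do not allow a count of events moved. At the interim, 8 of 50 subjects (16%) had a Grade 4 platelet count (Protocol 4.1.5), but how many would change column is unknown. A reader might scale that rate to 150 subjects and treat the result as a ceiling. The documents do not support this, because 9 of the 50 were still on study short of Week 24 and the final rate could be higher.

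A reader might also infer that the primary results are at risk. Changing how AEs are assigned to doses alters neither the overall Grade 4 proportion, nor its life table, nor the co-primary correlations. What final titrated dose to give a continuing subject on hold for all of Day 141 to 168 does bear on the co-primary dose variable. That is a separate question and no part of this point.

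**What to change.** - **SAP 5.2.** Remove the final-titrated-dose basis for AE summaries. Suggested text: *Final titrated dose groups (Section 5.9.3.1) are used for exposure and efficacy summaries only. In AE summaries by dose, each event is attributed to the last non-zero dose before the day of onset (Section 5.9.3.4); the column denominator is the number of subjects who ever took a dose in that band.* Say how a Day 1 event is assigned, since 5.9.3.4 looks only at earlier days.
- **Dose bands.** The exposure and efficacy shells use four bands (<5, >5 to 15, >15 to 25, >25 mg), not the six in 5.2. State which apply where.
- **Tables 14.3.3.6.1 and 14.3.3.6.2.** Make list title, shell title, column head and note name one rule. State one tie-break for repeat Grade 4 events: either first onset or the lowest onset dose. The second would match the lowest-dose-at-worst-grade note already in 14.3.2.1. Delete the crossover note.
- **Clerical.** In 14.3.2.2.2 the head over the dose columns reads CTCAE Grade and should name dose.

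The cost is a few sentences of SAP and shell wording. The dosing records and the 5.9.3.4 variable are already planned, so extra programming is small. No data collection or dosing rule changes.

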8.6.3.1. Restarting or Re-Escalating with Improving Platelet Counts

For subjects who had never previously increased their dose above 5 mg bid, and have a platelet count decline necessitating drug hold, ruxolitinib may be restarted as follows:

- Ruxolitinib may be restarted at 5 mg qd when the platelet count has risen above $35 \times 10^9/L$.
- After no less than 2 weeks, and provided there are at least 2 consecutive platelet count results, at least 3 days apart, of $\geq 40 \times 10^9/L$, the dose may be increased to 5 mg bid. No further increase in dose is allowed.
- A second platelet decline below $25 \times 10^9/L$ will necessitate a second drug hold. Ruxolitinib may be restarted at 5 mg qd when the platelet count has risen above $35 \times 10^9/L$. No further increase in dose is allowed.
 - The subject may remain on 5 mg qd provided platelet counts remain $\geq 25 \times 10^9/L$.

For subjects who had previously increased their dose to a level above 5 mg bid, and have a platelet count decline necessitating drug hold, ruxolitinib may be restarted as follows:

- Ruxolitinib may be restarted at 5 mg qd when the platelet count has risen above $35 \times 10^9/L$.
- After no less than 2 weeks, and provided there are at least 2 consecutive platelet count results, at least 3 days apart, of $\geq 40 \times 10^9/L$, the dose may be increased to a dose up to the highest dose that previously qualified for further dose increases according to [Section 8.6.1](#) (Dose Increases). For example, if a subject tolerated 10 mg bid ruxolitinib and qualified for a dose increase, but the platelet counts fell sharply at the increased dose of 10 mg AM/15 mg PM, and drug was halted; the highest dose this subject may now use is the previously tolerated dose of 10 mg bid.
- A second platelet decline below $25 \times 10^9/L$ will necessitate a second drug hold. Ruxolitinib may be restarted at 5 mg qd when the platelet count has risen above $35 \times 10^9/L$, and may be increased to 5 mg bid after ≥ 2 weeks with at least 2 consecutive measures above $40 \times 10^9/L$ at least 3 days apart. No further increase in dose is allowed.

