8.7. Withdrawal of Subjects from the Study

8.7.1. Withdrawal Criteria

Subjects may choose to withdraw from the study at any time without penalty of jeopardizing their health care or loss of benefits to which the subject is otherwise entitled. Every reasonable effort should be made to determine the reason a subject withdraws prematurely, and this information should be recorded in the eCRF.

A subject **may** be withdrawn from the study, if, in the investigator's expert medical judgment, the subject is non-compliant with the study requirements. Subjects may be withdrawn at the discretion of the Food and Drug Administration (FDA) or the investigator.

Subjects **must** be discontinued from study drug and withdrawn from the study for the following reasons:

- In the Investigator's medical judgment, further participation would be injurious to the subject's health or well-being
- Positive urine pregnancy test, confirmed by positive serum pregnancy (serum human chorionic gonadotropin) test results
- Consent is withdrawn
- Termination of the study by the sponsor, local health authority, or IRB/IEC.
- The subject requires splenic irradiation.
- The subjects exhibits leukemic transformation (as evidenced by bone marrow blast counts of at least 20%, or peripheral blast counts of at least 20% lasting at least 8 consecutive weeks).
- The subject cannot maintain platelet counts of at least $25 \times 10^9/L$ over a given 4 week interval at the lowest possible dose of 5 mg qd.
- The subject experiences 3 or more Grade 2 hemorrhage events. Note withdrawal after a second Grade 2 hemorrhage event may occur following the sponsor and investigator review of pertinent data.
- The subject experiences 2 hemorrhage events of \geq Grade 2, at least one of which is Grade 3 or Grade 4, and believed to be from the same source or etiology.

If a subject is withdrawn from the study:

- The study monitor or sponsor must be notified.
- The reason(s) for withdrawal must be documented in the subject's medical record and eCRF.
- The end-of-treatment/early termination visit should be performed.

- All subjects must be followed for safety until the time of the follow-up evaluation or until study drug related toxicities resolve, return to baseline or are deemed irreversible, whichever is longer.

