### 7.2. Secondary Endpoint(s) and Analyses

For the following secondary endpoints, descriptive summaries will be provided for overall as well as for the final titrated dose group:

- Percent change from baseline in spleen volume at Week 24.
- Percent change from baseline in total symptom score at Week 24.
- Proportion of subjects with  $\geq 35\%$  reduction from baseline in spleen volume at Week 24.
- Proportion of subjects with  $\geq 10\%$  reduction from baseline in spleen volume at Week 24.

- Proportion of subjects with  $\geq 50\%$  improvement from baseline in total symptom score at Week 24.
- Change and percentage change from baseline in spleen length as measured by palpation at each visit where the parameter is assessed.

Supporting data listings will also be provided.

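### The efficacy and exposure shells use dose columns that differ from SAP 5.2 and, as printed, leave a final titrated dose of exactly 5 mg/day in no column

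*SAP*

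**What the plan says.** SAP 5.2 (Treatment Groups) summarises subjects as one group. For certain adverse event summaries it sets six classes, "based on the final titrated total daily dose": <=5, >5-10, >10-15, >15-20, >20-25 and >25 mg. For exposure and efficacy its wording is permissive: "final titrated dose groups as defined above may be used as treatment groups and additional efficacy analysis may utilize these dose categories".

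SAP 7.2 is firmer about the secondary endpoints: "descriptive summaries will be provided for overall as well as for the final titrated dose group". Protocol 12.2.2 likewise promises summaries as one group and by final titrated dose. Neither section gives cut-points, so 5.2 is the only place in the SAP text that defines the group.

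In SAP Appendix B, the shells for Tables 14.2.2.1, 14.2.2.2, 14.3.1.1 and 14.3.1.3 are headed by final titrated dose and print `< 5`, `>5 to 15`, `>15 to 25` and `>25`. Programmer notes extend these layouts to Tables 14.2.2.3, 14.2.3.1, 14.2.3.2, 14.2.4.1 to 14.2.4.3, 14.2.5.1 and 14.3.1.2.

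SAP 5.9.3.1 defines the final titrated dose as the "average of the total daily dose (excluding periods of dose interruption) during the time interval of Day 141 and Day 168", or over the last 28 days of dosing data for early discontinuers. SAP 5.9.3.3 adds: "If prescribed dose collected from EX domain is 0, it also indicates a prescribed dose interruption".

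Protocol 8.7.1 refers to subjects "at the lowest possible dose of 5 mg qd". Protocol 8.6.3.1 provides for staying there after a second platelet-related hold: "The subject may remain on 5 mg qd provided platelet counts remain" at or above 25 x 10^9/L.

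**The concern.** The SAP carries two unreconciled groupings of the same variable, and the one in the shells is not exhaustive as printed. The lowest column stops below 5 and the next starts above 5, yet 5 mg/day is a dose at which a subject can finish the core phase. Protocol Table 2 reduces 5 mg bid to 5 mg qd and lets subjects continue there. Restarts after a platelet or ANC hold begin at 5 mg qd.

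At stake are the by-dose descriptive tables for spleen volume, symptom score, spleen length, PGIC and exposure. The study has a secondary objective on dosing strategy in patients with low platelets, and these tables bear on it. Subjects held at the bottom of the dose range would be missing from them without any note, and a reader adding the columns could find fewer subjects than the Total reports.

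**Working it through.** The plan states no figure for this point, and its sample size and power figures do not enter. The check is whether each attainable final dose has a column.

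**Inputs.** Tablets are 5 mg (Protocol 13.1). Increases are in steps of 5 mg/day, and the core-phase maximum is 15 mg bid, or 30 mg/day (Protocol 8.6.1). The lowest dose named is 5 mg qd (Protocol 8.7.1). The dose steps are therefore 5, 10, 15, 20, 25 and 30 mg/day.

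**Formula.** Final dose D = (sum of daily doses on days with a non-zero dose) / (number of such days). I assume that the zero-dose rule in SAP 5.9.3.3 also applies to the interruptions excluded in 5.9.3.1.

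**Assignment of each step:**

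| Dose, mg/day | SAP 5.2 class | Shell column as printed | Shell column if the lowest were `<=5` |
|---|---|---|---|
| 5 | <=5 | none | `<=5` |
| 10 | >5-10 | `>5 to 15` | `>5 to 15` |
| 15 | >10-15 | `>5 to 15` | `>5 to 15` |
| 20 | >15-20 | `>15 to 25` | `>15 to 25` |
| 25 | >20-25 | `>15 to 25` | `>15 to 25` |
| 30 | >25 | `>25` | `>25` |

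**Averages within a window.** If every non-zero daily dose is at least 5, then D is at least 5, and D = 5 only when every dosed day is at 5. One day at 10 moves the subject out of the hole: (27 x 5 + 1 x 10) / 28 = 145 / 28 = 5.18, which falls in `>5 to 15`. I enumerated all averages over 1 to 28 dosed days with at most one switch between two steps. The minimum was 5.0, and 5.0 was the only value with no shell column. Under the six classes of 5.2 no value was unassigned.

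**A separate gap.** A subject still on study but on hold for the whole window has zero dosed days, so D is undefined. No choice of cut-points places that subject in a column.

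**Effect of changing only the sign.** With `<=5` the four columns become exhaustive and are exact merges of neighbouring 5.2 classes: >5-10 with >10-15, and >15-20 with >20-25.

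**The case against.** The strongest reply is that the hole may not exist in the signed document. A column `>5 to 15` most naturally follows `<=5`, and an underlined `<` can lose its line when a PDF is read. Header damage does occur in this appendix: Table 14.3.2.2.2 appears under a CTCAE grade heading with a lowest column of 0 (N=2), where the companion Table 14.3.2.1 has `<=5` (N=2). Against this, `< 5` recurs in every four-column shell, while `<=30 Days` and `<=50` survive in the shell for Table 14.3.1.1. The question cannot be settled from the text available. If a sign was lost, the hole closes, but the shells still differ from 5.2 without explanation.

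Two further replies stand. First, a reader might infer that the shells break a SAP rule. They do not: 5.2 only permits its classes for exposure and efficacy, and 7.2 sets no cut-points. Second, a reader might infer that putting 20 and 25 mg/day in one column hides the response at 10 mg bid. The documents give no response rates by dose step from which to size or sign such an effect. The tables are descriptive, six columns would make some cells sparse, and a 28-day average does not isolate pure dose steps anyway. Four columns against six is a trade-off and not an error.

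It is also tempting to say that `< 5` must always be empty. The result above assumes the regular dose steps. The optional taper (Protocol 8.6.6) and the 50% reduction recommended with potent CYP3A4 inhibitors (Protocol 8.9.1) state no floor, so the documents do not exclude an average below 5. That does not give exactly 5 mg/day a column.

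**Conclusion.** The point holds for the boundary and for the mismatch. As printed, the four-column shells assign no column to a final titrated dose of exactly 5 mg/day, and they differ from the six classes in SAP 5.2. The hole catches only subjects whose dosed days in the window are all at 5 mg/day.

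The number of such subjects is not given. A reader might take the interim figure of 8 of 50 (16%) with Grade 4 platelet counts (Protocol 4.1.5) as a bound. It is not one: it counts any such laboratory value, not subjects staying at 5 mg qd through Day 141 to 168. Re-escalation after a first hold is allowed, and most interim subjects had reached 10 mg bid or higher by Week 24.

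The damage is limited to the by-dose secondary efficacy and exposure tables, and to the by-dose-group figures if they use the same columns. The co-primary correlations use dose as a continuous variable (SAP 7.1), so they, the scatter plots against dose and the Total column keep these subjects. Severity is minor to moderate. Confidence is moderate, because it rests on the printed `<` being what the authors wrote.

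**What to change.** 1. Check the sign in the source file. Set the lowest column to `<=5` in Tables 14.2.2.1, 14.2.2.2, 14.3.1.1 and 14.3.1.3, in every table programmed from them, and in the SAP 10.2 figures by final titrated dose group.
2. State one exhaustive set of cut-points in SAP 5.2 and use it in all these shells: either the six existing classes, or merges of adjacent 5.2 classes written out as such. A separate >15-20 mg/day column is optional.
3. Add a programming check that the column Ns, plus subjects with no defined final dose (for example, on hold for the whole window), sum to the Total. Report the undefined subjects in a footnote.

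The cost is an edit to the SAP text and shells, with no new data and no change to the primary analysis. The six-class option adds two columns, some likely to be sparse; the merged option avoids that.
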